ALTA is a health systems approach to improving medication adherence and BP control in primary care practices. It is designed to build practice capacity to address the needs of hypertensive patients by utilizing a team-based approach to delivering HTN care. ALTA includes five key components, which are conducted by existing members of the practice (Table 1): (1) Identify ALTA-eligible patients using hypertension registries. (2) Refer ALTA patients to a clinic Health Coach using the EHR. (3) Coach ALTA patients using a structured counseling tool integrated in the EHR to identify patients' treatment goals; assess their current level of BP control and medication adherence; identify barriers and facilitators to medication adherence; develop patient-centered adherence goals and action plans; and use a structured treatment algorithm to optimize patient antihypertensive medication regimen. (4) Document brief progress notes from the coaching session in the EHR to inform other team members of the patient's adherence status, action plans, progress toward goals, and any changes to the antihypertensive medication regimen. (5) Monitor and schedule follow-up sessions with ALTA patients in the EHR.

Table 1. ALTA components

ALTA components	ALTA Activities
Identify and Refer	
 • EHR registry to identify patients with uncontrolled HTN and non-adherent • EHR-based referral to MA/PCA/RN
Coach	
 • Structured assessment of medication adherence • Use of MINT to identify facilitators/barriers to adherence and discuss personalized strategies to improve adherence behaviors • Use of structured medication titration algorithm to optimize patient treatment regimen • Use of teach back to ensure patient understanding of treatment plan • Co-creation of culturally relevant goals and action plans
Document	
 • Structured documentation of coaching sessions in EHR to enable tracking patients' progress over time • EHR Documentation of individualized treatment plan, medication adherence goals, and action plan to guide future sessions and share with primary care provider for clinic visits
Monitor	
 • Consistent monitoring of patient progress through completion of and tracking follow-up sessions with ALTA patients

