Implementation quality of each ALTA component will be evaluated as the quality and content of data entry in the HTN registry, EHR-embedded coaching script, progress notes, and follow-up scheduling. Facilitators will rate the completeness of this form using a 3-point rating scale (1, poor; 2, adequate; 3, high). A random 10% sample of counseling sessions by the clinic Health Coaches will also be audiotaped and evaluated using the Health Coaching Evaluation Checklist, as we have done in our previous trials. A fidelity score will be calculated as the percentage of topics completed and how well they were delivered (1: poor skill performance, 2: adequate skill performance, 3: exemplary skill performance).

Participant responsiveness will be evaluated as patient and practice staff/provider satisfaction with ALTA and acceptability of practice changes with validated measures (i.e., ECHO survey for patients and a modified survey for staff/providers). In addition, qualitative interviews will be conducted with a random sample of clinic staff (n=30) and patients (n=30) across the practices to assess satisfaction with the intervention.

Program differentiation will be evaluated as the unique features of ALTA that are distinguishable from other programs at the sites. Throughout the study, facilitators will catalogue all initiatives that are occurring at the practices (as observed during site visits and/or reported by the practice leadership). This will be used to quantify the degree of overlap between the ALTA components and other quality improvement initiatives at the sites (1: no overlap, 2: some overlap, 3: significant overlap) as well as isolate the unique features of ALTA that distinguish it from those initiatives.

Secondary Outcomes

Workbench report will be requested from DataCore to include data from patients that have been diagnosed with hypertension and receiving care from the 10 safety-net practices. The workbench report will include PDC scores, demographics, B/P readings, medication list, and Voils medication adherence scores.

The ALTA workflow was built in Epic in coloration with MCIT. Therefore, we want to evaluate how the end-users (MAs, RNs, MDs, and PSAs) use the template built to enhance hypertension care at their sites. The data from the workbench report will be de-identified and analyzed in aggregate form to explore the primary outcome of Project ALTA.

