be rigorously trained on both the coding scheme and on the use of Atlas.ti. Initial coding by the coders will be reviewed by either [name] or [name] and any corrections to the coding will be made and/or additional coder training. Following this period, two coders will independently code at least 10 interviews. At this point we will establish the inter-rater reliability and if it is inadequate (Krippendorff's $\alpha < 0.80$) the Data Management and Analysis Subcommittee will work collaboratively to refine and/or clarify the coding scheme and provide additional coder training. Double coding will continue until adequate inter-rater reliability is achieved. Coding the data will allow us to fully describe the themes and the prevalence of specific themes and sub-themes. Following the procedures in our previous trials (e.g., ALMA trial), we will audiotape and archive MA-led health coaching sessions, of which 10% will be coded using the Health Coaching Evaluation Checklist. The checklist assesses the degree to which the MAs are correctly using their coaching techniques and are achieving the desired impact with patients. We will apply the same coding methods as the narrative reports and interviews. Briefly, two members of the study team will be rigorously trained by the Data Management and Analysis Subcommittee to apply the checklist to the tapes, and supervised by [name]. The coders will listen to the audiotapes twice, the first review will be done to get a sense of the session flow and MA counseling style; the second to code the interaction. We will establish inter-rater reliability after the two coders independently code at least 10 tapes, and double coding will continue until adequate inter-rater reliability is achieved (Krippendorff's $\alpha > 0.80$).

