Level of implementation adherence will be evaluated quantitatively as the degree to which the components of ALTA (e.g., identify, refer, coach, document, monitor) were implemented as intended, using data from checklists completed by the facilitators as well as extracted from the EHR. Each intervention component will be rated on a 3-point scale: 1=The component was not implemented, as per protocol; 2=The component was partially implemented; and 3=The component was fully implemented and/or modified with permission, as per protocol. We will calculate adherence as the number of components fully implemented (ratings of 3) divided by the total number of possible components ($N=8$). Practices will be considered adherent to the protocol if components were implemented completely and/or they were completed with an adaption that did not affect the programs core components and was approved by the study team. Facilitators will also complete monthly narrative reports that summarize all adaptations made to the components and what did/did not work for each practice context. We will also measure adherence through the Health Coaching Evaluation Checklist. The checklist will be used to count the parts of the standardized counseling script that were covered by the MAs at each health coaching session.

Part 2.

- Level of Implementation dose will be evaluated as the extent to which patients were exposed to ALTA. We will collect data on utilization patterns of the different ALTA components including the mean number of: ALTA-eligible patients identified in the registry and referred to a Health Coach; health coaching sessions completed with ALTA patients; entries in the EHR-embedded coaching script; progress notes

documented in the EHR and shared with the care team; and follow-up sessions that are scheduled and/or completed. System files will be extracted quarterly and will contain date and time stamps as well as user logins for the tools used. We will also calculate the average program dose, which is defined as all the number of times the MA-led health coaching sessions occurred during the implementation phase divided by the total number of patient encounters at the clinic during that same period of time (i.e., 12 months). To compare average dose across the practices, we will use a least square means analysis of variance (ANOVA) model with weighting by the number of patients seen in each practice within the specified time period.

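### The average program dose counts only MA-led coaching although ALTA allows referral to an MA, PCA or RN, so the between-practice dose comparison partly reflects staffing if coach mix differs; the taping frame is also defined two ways.

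*Combined protocol and SAP*

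**What the plan says.** **Who coaches.** Section 3.2 describes the referral step in role-neutral terms: "Refer ALTA patients to a clinic Health Coach using the EHR". Table 1 in that section spells out the recipients: "EHR-based referral to MA/PCA/RN".

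**Dose.** Section 6.4.3.1 first lists several utilization counts, among them "health coaching sessions completed with ALTA patients", entries in the coaching script, progress notes and follow-up sessions. None of these is limited by staff role. It then adds an average program dose, whose numerator is "all the number of times the MA-led health coaching sessions occurred during the implementation phase". The denominator is not restricted to coached patients or to any staff role: the count is "divided by the total number of patient encounters at the clinic during that same period of time". Only this ratio receives a formal comparison between practices: "To compare average dose across the practices, we will use a least square means analysis of variance (ANOVA) model", weighted by patients seen. The dose row of the fidelity table in section 6.1.4 likewise has facilitators log sessions with the MA.

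**Script coverage.** Under the adherence domain, sections 6.1.4 and 6.4.3.1 count the parts of the counseling script that MAs cover.

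**Taped quality sample.** In the account of qualitative coding, section 6.4.3.1 says "we will audiotape and archive MA-led health coaching sessions, of which 10% will be coded using the Health Coaching Evaluation Checklist". The quality row of the fidelity table also refers to MAs. By contrast, the definition of implementation quality in section 6.1.4, repeated in the quality bullet of section 6.4.3.1, draws the random 10% from sessions given by the clinic Health Coaches, without naming a role.

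**The concern.** Coaching by an RN or PCA is ALTA delivered as Table 1 describes it, yet such a session does not count toward the numerator of the average program dose. The encounters in the denominator are counted whoever does the coaching. The plan defines dose as patients' exposure to ALTA, and exposure does not depend on the coach's job title.

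Dose is one of the five domains of implementation fidelity, the primary outcome. If practices differ in who coaches, the ANOVA on average dose mixes staffing with delivery, and may place a practice that coaches more below one that coaches less. The ratio may also carry into the composite fidelity measure that section 6.4.3.1 relates to BP control and medication adherence.

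The conflicting taping frames raise a different risk: RN and PCA sessions may be absent from the tapes, so that coaching quality at some practices is judged on few sessions, on an unrepresentative set, or on none.

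**Working it through.** The plan states no figure for dose or coach mix, so there is nothing to reproduce. The check is arithmetic on the definition in section 6.4.3.1.

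**Notation for one practice over 12 months**
- S: all ALTA coaching sessions, by any coach
- E: all clinic encounters
- s: share of the S sessions led by MAs (not in the documents; shown from 0 to 1)

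**Formulas**
- Dose as written = (s × S) / E
- All-coach dose = S / E
- Ratio of the two = s, whatever S and E are

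Weighting the ANOVA by patients seen does not remove s, because the weights do not involve coach role.

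**Illustration of scale.** Section 5.3 gives over 800,000 annual visits. Spread evenly over 10 practices (assumption), E = 800,000 / 10 = 80,000. Take 70 coached patients (assumption, borrowed from the survey sample per clinic) with 4 sessions each (assumption): S = 70 × 4 = 280. The all-coach dose is 280 / 80,000 = 0.35%.

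| s | MA-led sessions | Dose as written | Share of all-coach dose | Tapes at 10% of MA sessions | Tapes at 10% of all sessions |
|---|---|---|---|---|---|
| 1 | 280 | 0.35% | 100% | 28 | 28 |
| 0.75 | 210 | 0.2625% | 75% | 21 | 28 |
| 0.5 | 140 | 0.175% | 50% | 14 | 28 |
| 0.25 | 70 | 0.0875% | 25% | 7 | 28 |
| 0 | 0 | 0% | 0% | 0 | 28 |

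With 1 session per patient the all-coach dose is 70 / 80,000 = 0.0875%; with 12 it is 840 / 80,000 = 1.05%. The shares in the fourth column do not change.

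**Ranking.** Practice A gives 280 sessions, all by MAs: 280 / 80,000 = 0.35%. Practice B gives 840 sessions with s = 0.25: 210 / 80,000 = 0.2625%. B delivers three times as much coaching and ranks below A. The session counts and the MA share are assumed; the example shows only that a reversal is possible.

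**Quality.** The taped score is a percentage of topics covered together with a 1-to-3 skill rating. It is not a count of sessions. Restricting the frame to MA sessions reduces the number of tapes, as in the table, but does not lower the score of any tape. Under the Health Coach wording all 28 remain.

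**The case against.** The strongest reply is that MA is shorthand for coach. Section 6.1.3 has facilitators train MAs on the counseling script and gives their conversion into coaches as an example of practice change; the self-efficacy measure in section 6.1.4 is framed around MAs. Only one line of Table 1 names a PCA or RN as a referral target, and no section reports any practice's coach mix. This stands as far as size goes: s may be 1 everywhere, and then the bias is zero. It does not rescue the wording. Table 1 lists the three roles separately, so an analyst who follows the numerator literally drops sessions that one who reads it as shorthand keeps.

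A reader might infer that practices coaching through RNs or PCAs will score low on dose and quality whatever they deliver. The documents do not support that. The utilization counts that precede the ratio in section 6.4.3.1 include those practices' sessions. Two of the four descriptions of the taped sample include their coaches, and the data-entry part of the quality rating has no role limit. Even on the MA-only reading, the consequence for tapes is missing or unrepresentative data.

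Nor does the statement in section 6.1.4 that "we want to evaluate how the end-users (MAs, RNs, MDs, and PSAs) use the template" show that RNs coach. It describes users of the Epic template, and that list includes physicians.

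The effect on the composite cannot be sized either. Section 6.4.3.1 gives no formula or weights for it, lets qualitative data prevail where sources diverge, and presents its link with clinical outcomes as something to explore.

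**Conclusion.** The mismatch holds for one measure, the average program dose. As written, that ratio is the all-coach dose multiplied by the practice's MA share, so it runs from 100% down to 0% of the all-coach value as the share falls from 1 to 0. The multiplier follows from the definition and needs no assumption about session or encounter counts. Whether it matters rests on one fact the documents omit: whether coach mix differs between practices. If it does, the ANOVA partly compares staffing. If the share is the same non-zero value everywhere, the relative comparison survives but the level is understated. If MAs do all the coaching, nothing is wrong numerically.

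The taping frame is a separate inconsistency that must be reconciled. Its possible consequence is a gap in quality data for RN and PCA coaches.

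**What to change.** - In section 6.4.3.1, define the numerator of the average program dose as coaching sessions led by any designated ALTA Health Coach (MA, PCA or RN).
- Use the same Health Coach term in the dose and quality rows of the fidelity table (section 6.1.4), in the script-coverage checklist (sections 6.1.4 and 6.4.3.1), and in every description of the taped 10% sample in those two sections.
- Optionally, report dose by coach role descriptively. The quarterly system files carry user logins, but the documents do not say that logins identify staff role, so this depends on a login-to-role lookup being available.

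The cost for dose is a change of wording, since the count of all completed coaching sessions is already collected. For taping it is also wording if the Health Coach frame is the one in use. If only MA sessions have been taped and other staff coach, including them takes some operational work, and any gap to date should be reported.

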5.1.2 Number of Study Sites

The study will be conducted at the network of 10 safety-net practices in New York.

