- Level of Implementation quality of each ALTA component will be evaluated as the quality and content of data entry in the HTN registry, EHR-embedded coaching script, progress notes, and follow-up scheduling. Facilitators will rate the completeness of this form using a 3-point rating scale (1, poor; 2, adequate; 3, high). A random 10% sample of counseling sessions by the clinic Health Coaches will also be audiotaped and evaluated using the Health Coaching Evaluation Checklist, as we have done in our previous trials. A fidelity score will be calculated as the percentage of topics completed and how well they were delivered (1: poor skill performance, 2: adequate skill performance, 3: exemplary skill performance).
- Level of responsiveness will be evaluated as patient and clinic staff/provider satisfaction with ALTA and acceptability for practice changes with validated measures (i.e., ECHO survey for patients and a modified survey developed by Lewis et al. for staff/providers). For both staff/provider and patient measures, we will calculate means and standard deviations for each scale across respondents within the practice. In addition, qualitative interviews will be conducted with a random sample of clinic staff (n=30) and patients (n=30) across the practices to assess satisfaction with the intervention. To compare responses across the practices, we will use a least square means ANOVA model with weighting by the number of respondents in each practice.
- Level of program differentiation will be evaluated as the unique features of ALTA that are distinguishable from other programs at the sites. Throughout the study, facilitators will catalogue all initiatives that are occurring at the practices (as observed during site visits and/or reported by the practice leadership). This will be used to quantify the degree of overlap between the ALTA components and other quality improvement initiatives at the sites (1: no overlap, 2: some overlap, 3: significant overlap as well as isolate the unique features of ALTA that distinguish it from those initiatives).

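### The dose ANOVA compares one 12-month ratio per practice across 10 practices and so has no error term; the responsiveness ANOVA needs its unit of analysis stated

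*Combined protocol and SAP*

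**What the plan says.** Section 6.4.3.1 (Primary Analyses) treats implementation fidelity, the primary outcome, domain by domain.

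**Dose.** Average program dose is the number of coaching sessions led by medical assistants in the implementation phase, "divided by the total number of patient encounters at the clinic during that same period of time (i.e., 12 months"). The comparison is then set out: "To compare average dose across the practices, we will use a least square means analysis of variance (ANOVA) model with weighting", the weight being "weighting by the number of patients seen in each practice within the specified time period". Earlier in the same bullet, on utilization data, the plan says "System files will be extracted quarterly and will contain date and time stamps as well as user logins for the tools used". It does not name quarter, patient or coach as the unit of the ANOVA.

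**Responsiveness.** Patients and staff complete satisfaction surveys individually. The plan says "we will calculate means and standard deviations for each scale across respondents within the practice", and then "To compare responses across the practices, we will use a least square means ANOVA model with weighting by the number of respondents" in each practice.

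**Number of practices.** Section 5.1.2: "The study will be conducted at the network of 10 safety-net practices in New York".

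The closing paragraph of 6.4.3.1 sets all tests at the two-sided 0.05 level. It names the treatment-by-time interaction as the primary test.

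**The concern.** An ANOVA across practices needs variation within practices to judge the differences between them. Dose, as defined, supplies none: each practice contributes one number for the whole 12 months. The weight, patients seen per practice, also points to practice-level rows.

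An analyst who reaches this step cannot run the stated model. A replicate unit or another test would have to be chosen after the data are in hand. That choice would affect a domain of the primary outcome. Dose and responsiveness are also the only two domains for which 6.4.3.1 gives a between-practice test; adherence, quality and differentiation have none.

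For responsiveness the question is narrower. The text does not say whether rows are respondents or practice means, and a weight equal to the number of respondents has a different effect in each case.

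**Working it through.** The plan states no degrees of freedom, F value or power for either ANOVA, so there is no figure to reproduce.

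**Inputs**
- Practices: k = 10 (section 5.1.2).
- Dose: one ratio per practice over 12 months (6.4.3.1).
- Patients surveyed: 70 per clinic x 10 = 700 (Synopsis, Number of Participants).
- Staff: 204 (section 5.3.1); expected survey response 70% (section 6.1.4, Moderator Variables).

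**Step 1: dose as written.** For a one-way model, residual df = rows - practices = 10 - 10 = 0. Each fitted value equals its own observation, so the weighted residual sum of squares is the sum of w_i(y_i - y_i)^2 = 0 for any weights w_i. The error mean square is 0/0 and F is undefined. A weighted fit to ten arbitrary values confirmed this: model df 9, residual df 0, residual sum of squares about 4e-27 (rounding error), F not a number.

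Reading the weight as a frequency does not help. Copies of the same value still have zero spread within a practice. Nor does the number of practices matter, since k - k = 0 for any k.

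**Step 2: dose with quarterly rows.** Rows = 10 x 4 = 40. Parameters = 1 intercept + 9 practice + 3 quarter = 13. Residual df = 40 - 13 = 27 (30 without the quarter terms).

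**Step 3: responsiveness with respondents as the unit.** Residual df = N - 10.

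| Respondents | N | Residual df | F critical value, 5% |
|---|---|---|---|
| Patients | 700 | 690 | 1.893 |
| Staff | 204 | 194 | 1.928 |
| Staff, if 70% of 204 respond | 143 | 133 | 1.951 |

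The practice summaries that the plan computes are enough to build this test. With practice means m_i, SDs s_i and sizes n_i,

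F = [sum n_i(m_i - m)^2 / (k - 1)] / [sum (n_i - 1)s_i^2 / (N - k)].

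On simulated data this gave 7.8916, the same as the ANOVA on the raw scores. With no true difference and 10 x 70 respondents, the unweighted test rejected in 4.9% of 4,000 replicates.

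**Step 4: the responsiveness weight on respondent rows.** Used as a precision weight, n_i asserts that an individual's score varies less in a larger practice. With equal n_i the constant cancels from F and nothing changes; simulation at 20 per practice gave 5.4% for both the weighted and the unweighted test. With unequal sizes it matters. Taking 6, 8, 10, 12, 15, 18, 22, 28, 35 and 50 (total 204; the split is an assumption, since the documents give no staff count per practice), the weighted test rejected in 0.85% of 2,000 null replicates, against 5.6% unweighted.

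**The case against.** The plan never writes down ten rows or a fixed practice factor; both are inferred. Time-stamped quarterly extracts exist, so replication is available for dose. Even the aggregate counts allow a Poisson homogeneity test on 9 df (critical value 16.92). These points show that dose can be compared in other ways, not that the stated ANOVA can be run. The average is defined over 12 months, the comparison is across practices, and no replicate unit is named. The Poisson test is a different analysis, and it would take the sessions as independent although patients have follow-up sessions.

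A reader might infer that the responsiveness ANOVA also has zero residual df. The documents do not support that. Scores come from individuals, within-practice SDs are planned, and it is responses that are compared. Weighting each squared deviation of a practice mean by n_i is also what the ordinary ANOVA formula does, so the wording is compatible with a valid test. Residual df would be 0 only if the SDs were discarded and ten means were the sole observations.

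A reader might also infer that the weight must badly distort the error rate. Rejection near 100% under the null appears only if each respondent row is counted n times, which the plan does not say. The loss of size in step 4 rests on assumed practice sizes, and patient samples are planned at an equal 70 per clinic.

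The limit on impact stands in full. The hypothesis in section 4.1 concerns facilitation against control, not differences among practices. The primary treatment-by-time test uses neither ANOVA, and practice ratios, means and SDs can still be reported.

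**Conclusion.** The dose ANOVA cannot be computed as written: 0 residual df, and no F-test, standard error or CI, whatever the weights. This rests on the plan's own definition of average dose and on reading the comparison across practices as making practice the factor, which is the natural reading.

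For responsiveness the defect is an unstated unit and a weight that is unnecessary at respondent level. A valid test with 690 (patients) or 194 (staff) residual df fits the text. The weight is harmless if practices contribute equal numbers and can distort the error rate if they do not.

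The consequence is confined to the between-practice comparison of these two domains. It is worth correcting because they belong to the primary outcome and the correction is cheap, but it does not threaten the trial's primary test.

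**What to change.** **Dose.** Replace the ANOVA with a regression of the count of coaching sessions per practice and quarter (40 rows), quasi-Poisson or negative binomial. Use log total patient encounters in that practice and quarter as offset, which keeps the plan's own denominator. Enter practice as the factor and quarter as a covariate, and report each practice's rate with a 95% CI. Define quarter from each practice's own start of implementation, since practices start at different times and each must contribute all four quarters for the 27 df to hold. The offset replaces the patients-seen weight.

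**Responsiveness.** State that individual respondents are the unit, with practice as the factor, and delete the weight by number of respondents.

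**Cost.** A few sentences of SAP text. Session data are already planned as quarterly, time-stamped extracts. The plan does not say that encounter totals are drawn by quarter, so these may need one further EHR query.

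**Downside.** Overdispersion is estimated from only 27 df, and quarters within a practice may be serially correlated, which would make the intervals too narrow if the correlation is positive. The SAP should say so.
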